9.3.6 Pregnancy and Exposure During Breastfeeding

Although pregnancy and infant exposure during breastfeeding are not considered adverse events, any pregnancy or infant exposure during breastfeeding in a participant (spontaneously reported to the investigator or their designee) that occurs during the study are reportable to the Sponsor.

All reported pregnancies must be followed to the completion/termination of the pregnancy. Pregnancy outcomes of spontaneous abortion, missed abortion, benign hydatidiform mole, blighted ovum, fetal death, intrauterine death, miscarriage and stillbirth must be reported as serious events (Important Medical Events). If the pregnancy continues to term, the outcome (health of infant) must also be reported.

9.3.7 Events of Clinical Interest (ECI)

Selected non-serious and serious adverse events are also known as Events of Clinical Interest (ECI) and must be reported to the Sponsor.

Events of clinical interest for this study include:

1. an elevated AST or ALT lab value that is greater than or equal to 3X the upper limit of normal and an elevated total bilirubin lab value that is greater than or equal to 2X the upper limit of normal and, at the same time, an alkaline phosphatase lab value that is less than 2X the upper limit of normal, as determined by way of protocol-specified laboratory testing or unscheduled laboratory testing.*

*Note: These criteria are based upon available regulatory guidance documents. The purpose of the criteria is to specify a threshold of abnormal hepatic tests that may require an additional evaluation for an underlying etiology. The study site guidance for assessment and follow up of these criteria can be found in the Investigator Trial File Binder (or equivalent).

9.4 Treatment of Overdose

In this study, an overdose is any dose >1 tablet BID in Stage 1 and Stage 2 (if only 2 treatment arms are included). If a 3rd treatment arm is added in Stage 2 based on the results of the efficacy IA, an overdose will be defined as >2 tablets BID (Section 7.1).

No specific information is available on the treatment of overdose. Oral doses of up to 1800 mg BID for 14 days were explored in earlier clinical studies without any untoward clinical effects [IB Edition 16 2017]. Overdoses should be treated according to the participant's clinical signs and symptoms.

Decisions regarding dose interruptions or modifications will be made by the investigator in consultation with the Sponsor Clinical Director based on the clinical evaluation of the participant.

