5.5 Justification for Dose

5.5.1 Rationale for Dose Interval and Study Design

In this trial, MK-7264 45 mg (and potentially MK-7264 15 mg if an additional treatment arm is added in Stage 2) will be orally administered in tablet form BID based on the safety and PK efficacy results observed to date.

Based on PK studies conducted to date, MK-7264 is rapidly absorbed with a median T_{max} of 1 to 2 hours and a half-life of approximately 7 to 10 hours, and is consistent with a BID dosing schedule.

In the clinical development program, oral doses of MK-7264 up to 1800 mg BID for 14 days were evaluated in Phase 1 studies and oral doses of up to 600 mg BID have been evaluated in Phase 2 studies. Overall, MK-7264 has been generally safe and well tolerated. Across studies, taste-related AEs (eg, dysgeusia, ageusia, hypogeusia) and tingling sensation in the mouth and/or throat were the most frequently reported events. These AEs have been reversible and are amenable to monitoring.

In participants with chronic cough, improved tolerability (relative to higher doses of MK-7264) and efficacy have been observed at doses of MK-7264 ≤ 50 mg BID. Doses from 7.5 mg to 200 mg BID were studied in participants with chronic cough (in P010 Cohort 1)

and 50 mg BID was as effective as higher doses; however, doses higher than 50 mg BID were associated with less tolerability.

The mechanism of action of MK-7264 and related clinical study results demonstrate that the efficacy of MK-7264 in decreasing cough, and the prevalence of the most common AE, dysgeusia, are both dose-related. In order to provide patients and prescribers the flexibility to balance efficacy and tolerability based on individual clinical situations, the MK-7264 development program has targeted two doses (15 mg BID and 45 mg BID) to study.

The 45 mg BID dose has been selected for Stage 1 of this trial to evaluate whether this dose will effectively reduce acute cough with a side effect profile that is tolerable to patients. During Stage 2 of the trial (after the efficacy IA), a third treatment group with a lower dose of MK-7264 (15 mg BID) may be added, based on the results of the IA and PK modeling, taking both efficacy and safety/tolerability into consideration.

For additional details on MK-7264, refer to the IB (Section 3.2).

6. Study Population

Healthy male and female participants between the ages of 18 and 55 years (inclusive) will be enrolled in this study.

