7.1 Treatments Administered

The study treatments to be used in this study are outlined below in [Table 1](#) and administered as shown in [Table 2](#).

Table 1 Study Treatments

Study Treatment Name:	MK-7264 45 mg BID	MK-7264 15 mg BID	Placebo
Dosage Formulation:	Tablet	Tablet	Tablet
Unit Dose Strength(s):	45 mg	15 mg	Placebo to match each of MK-7264 45 mg and 15 mg ^a
Dosage Level(s):	45 mg BID	15 mg BID	Placebo to match MK-7264 45 mg BID and 15 mg BID ^a
Route of Administration:	Oral	Oral	Oral
Sourcing:	Provided centrally by the Sponsor	Provided centrally by the Sponsor	Provided centrally by the Sponsor

Abbreviations: BID = twice daily

^a As the images of MK-7264 45 mg and 15 mg are not identical, the placebo to match MK-7264 45 mg is different than the placebo to match MK-7264 15 mg.

Table 2 Treatment Administration

Period	Trial Day	Double-Blinded Study Treatment Stage 1 ^a	Double-Blinded Study Treatment ^a Stage 2 ^b
Treatment Period	1	MK-7264 45 mg BID or Placebo	MK-7264 45 mg BID or MK-7264 15 mg BID ^c or Placebo
	2		
	3		
	4		
	5		
	6		
	7		

Abbreviations: BID = twice daily; IA = interim analysis.

^a Stage 1 - Prior to efficacy IA.

^b Stage 2 - Post-efficacy IA.

^c MK-7264 15 mg BID group applicable only if a decision is made to add a lower dose of MK-7264 based on results of the efficacy IA.

All supplies indicated in [Table 1](#) will be provided per the ‘Sourcing’ row depending upon local country operational requirements. Every attempt should be made to source these supplies from a single lot/batch number. The study site is responsible for recording the lot number, manufacturer, and expiry date for any locally purchased product (if applicable) as per local guidelines unless otherwise instructed by the Sponsor.

Refer to Section 9.1.8 for details regarding administration of the study treatment.

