7.6 Treatment Compliance

Randomized participants will remain in the clinic throughout the Treatment Period until Day 7 (or discontinuation). Administration of all study treatments will be witnessed by the investigator and/or study staff.

During the Treatment Period in Stage 1, all participants will receive 1 tablet of MK-7264 45 mg or placebo BID.

During the Treatment Period in Stage 2 (post-efficacy IA), if there are:

- Two treatment arms: all participants will receive 1 tablet of MK-7264 45 mg or placebo BID.

- Three treatment arms: all participants will receive 1 tablet of MK-7264 45 mg and 1 tablet of placebo for MK-7264 15 mg OR 1 tablet of MK-7264 15 mg and 1 tablet of placebo for MK-7264 45 mg OR 1 tablet of placebo for MK-7264 45 mg and 1 tablet of placebo for MK-7264 15 mg, BID.

Interruptions from the protocol specified treatment plan for >1 day require consultation between the investigator and the Sponsor and written documentation of the collaborative decision on participant management.

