9.1.8 Treatment Administration

Throughout the treatment period, administration of study treatment (all doses) will be witnessed by the investigator and/or study staff.

Study treatment will begin in the morning (before 11 am approximately) on the day of treatment randomization (Day 1). After randomization, the study participant will first have the VitaloJAK™ attached. The participant will then be inoculated with HRV-16 and then administered the first dose of study treatment. The VitaloJAK will then be immediately turned “on” after the first dose is administered. As dosing is BID, the next dose of study treatment on Day 1 should be taken orally in the evening, approximately 12 hours after the morning dose. Subsequent dosing through Day 7 will be performed in the same manner.

In Stage 1, all participants will be administered 1 tablet of study treatment BID (total daily dose: 2 tablets).

In Stage 2, if there are 2 treatment arms, all participants will be administered 1 tablet BID (total daily dose: 2 tablets). If there are 3 treatment arms (in order to maintain the blinding of the 2 different MK-7264 dose images), all participants will be administered 2 tablets of study treatment BID (totally daily dose: 4 tablets).

For more details about treatment compliance, see Section 7.6.

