Type of Event	Reporting Time Period: Consent to Randomization/ Allocation	Reporting Time Period: Randomization/ Allocation through Protocol-Specified Follow-up Period	Reporting Time Period: After the Protocol Specified Follow-up Period	Timeframe to Report Event and Follow-up Information to SPONSOR:
Cancer	Report if: - due to intervention - causes exclusion	Report all	Not required	Within 5 calendar days of learning of event
Overdose	Report if: - receiving placebo run-in or other run-in medication	Report all	Not required	Within 5 calendar days of learning of event

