
• An AE is any untoward medical occurrence in a patient or clinical study participant, temporally associated with the use of study treatment, whether or not considered related to the study treatment.• NOTE: An AE can therefore be any unfavorable and unintended sign (including an abnormal laboratory finding), symptom, or disease (new or exacerbated) temporally associated with the use of a study treatment.• NOTE: for purposes of AE definition, study treatment (also referred to as Sponsor's product) includes any pharmaceutical product, biological product, vaccine, device, diagnostic agent or protocol specified procedure whether investigational (including placebo or active comparator product) or marketed, manufactured by, licensed by, provided by or distributed by the sponsor for human use in this study.

Events Meeting the AE Definition

• Any abnormal laboratory test results (hematology, clinical chemistry, or urinalysis) or other safety assessments (eg, ECG, radiological scans, vital signs measurements), including those that worsen from baseline, or are considered clinically significant in the medical and scientific judgment of the investigator.• Exacerbation of a chronic or intermittent pre-existing condition including either an increase in frequency and/or intensity of the condition.• New conditions detected or diagnosed after study treatment administration even though it may have been present before the start of the study.• Signs, symptoms, or the clinical sequelae of a suspected drug-drug interaction.• Signs, symptoms, or the clinical sequelae of a suspected overdose of either study treatment or a concomitant medication.• For all reports of overdose (whether accidental or intentional) with an associated adverse event, the AE term should reflect the clinical symptoms or abnormal test result. An overdose of study treatment without any associated clinical symptoms or abnormal laboratory results is reported using the terminology "accidental or intentional overdose without adverse effect."• Any new cancer or progression of existing cancer.

Events NOT Meeting the AE Definition

- Medical or surgical procedure (eg, endoscopy, appendectomy): the condition that leads to the procedure is the AE.
- Situations in which an untoward medical occurrence did not occur (social and/or convenience admission to a hospital).

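### If the 15 mg arm is added, the overdose rule counts total tablets only, so two tablets of the active image in place of one of each (twice the assigned dose) is not an overdose

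*Combined protocol and SAP*

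**What the plan says.** Section 9.4 holds the only definition of overdose in the protocol. With two arms, "an overdose is any dose >1 tablet BID in Stage 1 and Stage 2 (if only 2 treatment arms are included". If the third arm is added, "an overdose will be defined as >2 tablets BID". Neither version refers to tablet image or to milligrams of active drug.

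The three-arm regimen is double-dummy. Section 7.6 gives the composition for the 45 mg group: "all participants will receive 1 tablet of MK-7264 45 mg and 1 tablet of placebo for MK-7264 15 mg". The 15 mg and placebo groups follow the same one-of-each pattern. Section 9.1.8 confirms the count: "all participants will be administered 2 tablets of study treatment BID (totally daily dose: 4 tablets". The two images can be told apart, since the Table 1 footnote in Section 7.1 says that "the placebo to match MK-7264 45 mg is different than the placebo to match MK-7264 15 mg".

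Table 3 requires every overdose after randomization to be reported, with the timeframe "Within 5 calendar days of learning of event". Appendix 4 extends this to events without consequences: "An overdose of study treatment without any associated clinical symptoms or abnormal laboratory results is reported using the terminology" a set phrase for overdose without adverse effect.

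**The concern.** The threshold moves from one tablet to two when the second image is introduced, but the rule does not follow the structure of the regimen. A dose is no longer a number of like tablets; it is one of each of two kinds. A count of the total cannot separate the correct pair from two of the same kind.

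If staff give two tablets of one image and omit the other, the total is two and Section 9.4 records no overdose. Where the duplicated image is the active one, the participant has taken twice the assigned active dose. What is lost is a report the protocol requires, chiefly for the event without symptoms that Appendix 4 takes care to include. Section 5.5.1 gives some reason to care about the 45 mg case, because in chronic cough "doses higher than 50 mg BID were associated with less tolerability", although that statement concerns repeated dosing and not one 90 mg dose.

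**Working it through.** **Inputs.** Tablets per dose and their composition: Sections 7.6 and 9.1.8. Overdose thresholds: Section 9.4. Allocation of 1:2:1 (45 mg : 15 mg : placebo) in a three-arm Stage 2: Section 7.3. Total of 150 with the added arm, of whom about 50 are in Stage 1: Table 10 and Section 5.1.

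**Planned count.** One tablet of each image is 1 + 1 = 2 per dose, and 2 × 2 = 4 per day. This agrees with Section 9.1.8.

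**Which combinations the rule misses.** Let *a* be the number of 45 mg-image tablets and *b* the number of 15 mg-image tablets taken at one dose.

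- Current rule: overdose if *a* + *b* > 2.
- Per-image rule: overdose if *a* > 1 or *b* > 1.

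If neither *a* nor *b* exceeds 1, the sum cannot exceed 2, so every case the current rule catches is also caught by the per-image rule. The cases caught only by the per-image rule have *a* > 1 or *b* > 1 with a sum of at most 2: (2,0) and (0,2), and no others.

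| Tablets (*a*, *b*) | 45 mg arm | 15 mg arm | Placebo | Total > 2? |
|---|---|---|---|---|
| (1,1) planned | 45 mg | 15 mg | 0 | no |
| (2,0) | 2 × 45 = 90 mg (200%) | 0 mg | 0 | no |
| (0,2) | 0 mg | 2 × 15 = 30 mg (200%) | 0 | no |
| (2,1) | 90 mg | 15 mg | 0 | yes |
| (1,2) | 45 mg | 30 mg | 0 | yes |

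The 90 mg dose is therefore an overdose when it comes from (2,1) but not when it comes from (2,0). In Stage 1, 90 mg at one dose is two tablets, which is more than one, and counts as an overdose. Reading the threshold per day does not help: (2,0) at one dose and (1,1) at the other is 4 tablets, the planned daily number.

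**How such errors would divide.** Stage 2 has 150 − 50 = 100 participants, or 25/50/25 at 1:2:1. The documents give no error rate. Assume each participant is equally likely to have the error, and let *q* be the probability that the duplicated image is the 45 mg one.

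- Active dose doubled: (25*q* + 50(1 − *q*))/100. This is 0.375 at *q* = 0.5, 0.50 at *q* = 0 and 0.25 at *q* = 1.
- Active-arm participant given no active drug, at *q* = 0.5: (25 × 0.5 + 50 × 0.5)/100 = 0.375.
- Placebo participant: 25/100 = 0.25.

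At *q* = 0.5, the share that does not double an active dose is 0.375 + 0.25 = 0.625.

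**The case against.** The strongest case against is about weight. The siDMC must first add the arm. Staff must then give two visibly alike tablets where the regimen calls for two different ones, with every dose witnessed, and the participant must be in the arm where that image is active. How tablets are packed per dose is not described, so the feasibility of the error cannot be judged from the documents. Of the 37.5% that double the active dose, 25 × 0.5/100 = 12.5% are in the 45 mg arm and 50 × 0.5/100 = 25% in the 15 mg arm. The latter receive 30 mg, less than the 45 mg arm takes at every dose, so only the 45 mg-arm case exceeds the trial's highest assigned dose. Section 9.4 itself cites 1800 mg BID for 14 days without untoward clinical effects. Adverse events are reported regardless, drug accountability should expose image miscounts, and the error could be recorded as a protocol deviation. Finally, the Stage 1 comparison concerns a different error, an extra tablet, which the three-arm rule also catches.

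All of this stands as a limit on importance. None of it supplies a per-image or milligram rule or shows that the omission was intended. The point that a per-image rule would flag doses with no excess active drug is also true, but the present rule already does so: in the 45 mg arm, (1,2) is flagged at the correct 45 mg, and in placebo any three tablets are flagged.

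**Conclusion.** The gap is real and follows from the wording alone. In a three-arm Stage 2, Section 9.4 classes a doubled active dose as no overdose when it arises by same-image substitution: 90 mg for 45 mg, or 30 mg for 15 mg. Two combinations per dose are affected. The 37.5% share, and its range of 25% to 50%, rests on the assumed equal risk per participant and on the image split, not on anything in the documents. The number of such errors is unknown and should be low.

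The consequence is a missed overdose report, mainly for events without symptoms. Overdose is not a category in Table 7, and no efficacy analysis, sample size or planned safety comparison is affected. This is a minor correction, worth making because it is cheap and because Stage 2 cannot start until the pause for the interim analysis is over.

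**What to change.** In Section 9.4, for the three-arm case, define overdose as more than one tablet of either image at a dosing occasion. Leave the Stage 1 and two-arm rule, the doses and the care of an overdose as they are. Because the images differ, site staff can apply the rule without knowing which tablet is active.

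The cost is one sentence and the matching eCRF guideline, plus a few more blinded reports. Under the equal-risk assumption about 62.5% of those would not be a doubled active dose: 25% in placebo and 37.5% in active-arm participants who received no active drug at that dose. They can be sorted out after unblinding. The documents describe no such step, so the guideline should say so in a line.

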9.5 Safety

Details regarding specific safety procedures/assessments to be performed in this study are provided below.

Planned time points for all safety assessments are provided in the SoA.

9.5.1 Physical Examinations

All participants will undergo a full physical examination (except for rectal and genital examination) at the visits specified in the SoA (Section 2).

The full examination will be conducted as per institutional standard on the following body systems: general appearance, head (ie, oral inspection, ears, eyes, nose, and throat), respiratory (ie, auscultation/stethoscope examination of the lungs), heart (ie, auscultation/stethoscope examination of the heart), abdomen, musculoskeletal, neurological, lymph nodes, and skin. Participants with evidence of current, clinically significant, intercurrent illness (eg, significant cold or flu) may be rescheduled for rescreening upon resolution of their illness (See Section 9.10.1.1).

Based on investigator judgment, questioning regarding symptoms may be sufficient for the following body systems: abdomen, urogenital, musculoskeletal, and neurological. If deemed necessary by the investigator, a physical examination of these body systems will be performed.

Investigators should pay special attention to clinical signs related to previous serious illnesses.

A physical exam (full or limited) may be performed at any clinic visit that does not already include a physical exam or at any unscheduled visit if deemed necessary by the investigator due to signs/symptoms.

Clinically significant changes from baseline will be recorded as AEs. Baseline for physical examination is defined as the examination performed during the Screening Visit.

9.5.2 Vital Signs and Weight and Height Measurements

Vital signs (including oral body temperature (centigrade), blood pressure (mm Hg), pulse rate (beats per minute), and respiratory rate (breaths per minute)), height (cm), and weight (kg) will be assessed at the visits specified in the SoA (Section 2). All vital signs will be measured after each participant has been sitting/resting for at least 5 minutes. Blood pressure measurements should be performed on the same arm, preferably by the same person. At the Screening Visit, vital signs will be measured just before the spirometry measurement.

Any clinically significant abnormalities in vital signs noted after the Screening Visit will be recorded as AEs in the AE eCRF.

9.5.3 Electrocardiograms

A single 12-lead ECG will be obtained as outlined in the SoA (Section 2) using local standard procedures. Clinically significant abnormal findings should be recorded in the AE eCRF.

9.5.4 Spirometry

A spirometry assessment will be performed at the Screening Visit using a local calibrated spirometer.

Spirometry should be performed in accordance with guidelines established by ATS/ERS (Available from: <http://www.thoracic.org/statements>). For safety reasons, spirometry should be performed with the participant sitting, using a chair with arms and without wheels; however, if necessary to undertake the testing with the participant standing or in another position, this should be noted on the spirometry report.

9.5.5 Taste-Related Adverse Events

The tolerance to taste-related AEs will be evaluated during the study if a taste-related AE(s) is reported. At the time the taste-related AE is reported and every day until the AE is reported as resolved, the site staff will obtain information on the timing, duration, intensity, etc., of the taste-related AE.

The information will be entered into the appropriate eCRFs based on the eCRF entry guidelines, which will be provided to the sites by the Sponsor.

9.5.6 Clinical Safety Laboratory Assessments

Refer to Appendix 5 for the list of clinical laboratory tests to be performed and to the SoA for the timing and frequency.

- The investigator must review the laboratory report, document this review, and record any clinically relevant changes occurring during the study in the AE section of the CRF. The laboratory reports must be filed with the source documents. Clinically significant abnormal laboratory findings are those which are not associated with the underlying disease, unless judged by the investigator to be more severe than expected for the participant's condition.
- All protocol-required laboratory assessments, as defined in Appendix 5, must be conducted in accordance with the Central Laboratory Manual and the SoA (Section 2).
- If laboratory values from non-protocol specified laboratory assessments performed at the institution's local laboratory require a change in study participant management or are considered clinically significant by the investigator (eg, SAE or AE or dose modification), then the results must be recorded in the appropriate CRF (eg, SLAB).
- For any laboratory tests with values considered clinically significantly abnormal during participation in the study or within 14 days after the last dose of study treatment, every attempt should be made to perform repeat assessments until the values return to normal or baseline or if a new baseline is established as determined by the investigator.

